7.8. Treatment after the End of the Study

After the conclusion of the study, continued access to baricitinib will not be provided. Patients will be referred to their local treatment centers for AD therapy as clinically indicated.

8. Discontinuation Criteria

8.1. Discontinuation from Study Treatment

8.1.1. Temporary Discontinuation from Study Treatment

In some circumstances, it may be necessary to temporarily interrupt treatment as a result of AEs or abnormal laboratory values that may have an unclear relationship to IP. For example, IP should be temporarily interrupted if the patient experiences a cardiovascular adverse event considered to be related to study treatment, is graded as moderate (Grade 2 according to Common Terminology Criteria for Adverse Events [CTCAE] Version 3.0), and that does not resolve promptly with supportive care. Except in cases of emergency, it is recommended that the investigator consult with Lilly (or its designee) before temporarily interrupting therapy for reasons other than those defined in [Table JAIP.5](#).

For the abnormal laboratory findings and clinical events (regardless of relatedness) listed in [Table JAIP.5](#), specific guidance is provided for temporarily interrupting treatment and when treatment may be restarted. Retest frequency and timing of follow-up laboratory tests to monitor the abnormal finding is at the discretion of the investigator. Investigational product that was temporarily interrupted because of an AE or abnormal laboratory value not specifically covered in [Table JAIP.5](#) may be restarted at the discretion of the investigator.

Table JAIP.5. Criteria for Temporary Interruption of Investigational Product

Hold Investigational Product if the Following Laboratory Test Results or Clinical Events Occur:	Investigational Product May Be Resumed When:
WBC count <2000 cells/ μ L (<2.00x10 ³ / μ L or <2.00 GI/L)	WBC count \geq 2500 cells/ μ L (\geq 2.50x10 ³ / μ L or \geq 2.50 GI/L)
ANC <1000 cells/ μ L (<1.00x10 ³ / μ L or <1.00 GI/L)	ANC \geq 1200 cells/ μ L (\geq 1.20x10 ³ / μ L or \geq 1.20 GI/L)
Lymphocyte count <500 cells/ μ L (<0.50x10 ³ / μ L or <0.50 GI/L)	Lymphocyte count \geq 750 cells/ μ L (\geq 0.75x10 ³ / μ L or \geq 0.75 GI/L)
Platelet count <75,000/ μ L (<75x10 ³ / μ L or <75 GI/L)	Platelet count \geq 100,000/ μ L (\geq 100x10 ³ / μ L or \geq 100 GI/L)
eGFR <50 mL/min/1.73 m ² (from serum creatinine)	eGFR \geq 60 mL/min/1.73 m ²
ALT or AST >5x ULN	ALT and AST return to <2x ULN, and IP is not considered to be the cause of enzyme elevation
Hemoglobin <8 g/dL (<80.0 g/L)	Hemoglobin \geq 10 g/dL (\geq 100.0 g/L)
Symptomatic herpes zoster (shingles or chicken pox)	All skin lesions have crusted and are resolving
Infection that, in the opinion of the investigator, merits the IP being interrupted	Resolution of infection
Clinical features of VTE (such as deep vein thrombosis or pulmonary embolism) are present ^a	After ruling out event of VTE

Abbreviations: ALT = alanine aminotransferase; ANC = absolute neutrophil count; AST = aspartate aminotransferase; eGFR = estimated glomerular filtration rate; GI = billion; IP = investigational product; ULN = upper limit of normal; VTE = venous thromboembolic event; WBC = white blood cell.

^a Evaluate promptly and institute appropriate treatment. If upon evaluation VTE is ruled out and no other temporary or permanent discontinuation criteria are met, then IP may be resumed.

Although temporary interruption of IP is not a requirement at times of increased potential risk of VTE (e.g., surgery, significant air travel, or other situations involving prolonged immobilization), following appropriate VTE prophylaxis guidelines is recommended to help manage the VTE risk under these circumstances.

If rescue with phototherapy is required during Study Period 4, then the IP must be temporarily interrupted until the phototherapy treatments have been completed (see Section 7.7.5, Rescue Therapy).

During the long-term extension the patient will be allowed to receive live vaccines with appropriate interruption of baricitinib treatment prior to and after the live vaccine (see Section 7.7.4).

Lastly, IP should be temporarily interrupted for suicidal ideation or any suicide-related behaviors as assessed by the following patient responses on the C-SSRS:

- A “yes” answer to Question 4 (Active Suicidal Ideation with Some Intent to Act, Without Specific Plan) **or**
- A “yes” answer to Question 5 (Active Suicidal Ideation with Specific Plan and Intent) on the "Suicidal Ideation" portion of the C-SSRS **or**

- A "yes" answer to any of the suicide-related behaviors (actual attempt, interrupted attempt, aborted attempt, preparatory act or behavior) on the "Suicidal Behavior" portion of the C-SSRS.

NOTE: Prior to resumption of IP, it is recommended that the patient be assessed by a psychiatrist or appropriately trained professional to assist in deciding whether the subject should remain on IP and ultimately continue participation in the study. A patient does not necessarily have to have IP interrupted if they have self-injurious behavior that would be classified as non-suicidal self-injurious behavior.

8.1.2. Permanent Discontinuation from Study Treatment

Investigational product should be permanently discontinued if the patient or the patient's designee (parent/legal guardian/caregiver) requests to discontinue IP.

Discontinuation due to a hepatic event or liver test abnormality.

Patients who are discontinued from IP due to a hepatic event or liver test abnormality should have additional hepatic safety data collected via case report form (CRF) or other designated data transmission methods.

Discontinuation of the IP for abnormal liver tests **should be** considered by the investigator when a patient meets one of the following conditions after consultation with the Lilly designated medical monitor:

- ALT or AST $>8\times$ ULN
- ALT or AST $>5\times$ ULN for more than 2 weeks
- ALT or AST $>3\times$ ULN and total bilirubin level (TBL) $>2\times$ ULN or international normalized ratio (INR) >1.5
- ALT or AST $>3\times$ ULN with the appearance of fatigue, nausea, vomiting, right upper quadrant pain or tenderness, fever, and/or rash
- ALP $>3\times$ ULN (unless allowed after discussion with Sponsor)
- ALP $>2.5\times$ ULN and TBL $>2\times$ ULN
- ALP $>2.5\times$ ULN with the appearance of fatigue, nausea, vomiting, right quadrant pain or tenderness, fever, and/or rash

Investigational product should be permanently discontinued if any of the following laboratory abnormalities are observed:

- white blood cell count <1000 cells/ μ L ($1.00\times 10^3/\mu$ L or 1.00 GI/L)
- ANC <500 cells/ μ L ($0.50\times 10^3/\mu$ L or 0.50 GI/L)
- lymphocyte count <200 cells/ μ L ($0.20\times 10^3/\mu$ L or 0.20 GI/L)
- hemoglobin <6.5 g/dL (<65.0 g/L).

NOTE: Temporary interruption rules (see Section 8.1.1) must be followed where applicable. For laboratory values that meet permanent discontinuation thresholds, IP should be discontinued. However, if in the opinion of the investigator the laboratory abnormality is due to intercurrent illness such as cholelithiasis or another identified factor, laboratory tests may be repeated. Only when the laboratory value meets resumption thresholds (Table JAIP.5) following the resolution of the intercurrent illness or other identified factor may the investigator restart IP, after consultation with the Lilly-designated medical monitor.

In addition, patients will be discontinued from IP in the following circumstances:

- pregnancy
- malignancy
- hepatitis B virus DNA is detected with a value above the limit of quantitation or 2 sequential tests return a value of below the limit of quantitation (see Section 9.4.8).
- develop a VTE event

If a patient who is participating in the Double-blind Treatment period (Study Period 3) discontinues IP for any reason, the patient is encouraged to remain in the study through Week 16 (Visit 8) and follow the regular visit schedule to provide the primary efficacy and safety data. Patients discontinuing from the IP prematurely for any reason should complete AE and other follow-up procedures per Section 2 (Schedule of Activities), Section 9.2 (Adverse Events), and Section 9.4 (Safety) of this protocol.

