Appendix 7. Liver Function Testing and Hepatic Safety Monitoring

Liver Function Testing and Hepatic Safety Monitoring

Analyte	Exclusion Criteria	Additional Hepatic Testing	Hepatic eCRF Reporting	Temporary Interruption of IP	Permanent Discontinuation of IP after Consultation with the Lilly-Designated Medical Monitor
Protocol Section	Section 6.2	Section 9.4.9.1	Section 9.4.9.1	Section 8.1.1	Section 8.1.2
ALT/AST	≥2x ULN	ALT ≥3x ULN	ALT ≥5x ULN on ≥2 consecutive tests	>5x ULN	
 • >8x ULN • >5x ULN for >2 weeks • >3x ULN AND TBL >2x ULN or INR >1.5 • >3x ULN with symptoms^a
ALP	≥2x ULN (unless allowed after discussion with Sponsor)	≥2x ULN (for patients with baseline <2x ULN)	≥2x ULN on ≥2 consecutive tests (for patients with baseline <2x ULN)	No applicable criteria	
 • >3x ULN (unless allowed after discussion with Sponsor) • >2.5x ULN AND TBL >2x ULN • >2.5x ULN with symptoms^a
TBL	≥1.5x ULN (unless allowed after discussion with Sponsor)	≥2x ULN (for patients with baseline <1.5 ULN)	≥2x ULN (excluding Gilbert's syndrome)	No applicable criteria	
 • ALT or AST >3x ULN AND TBL >2x ULN • ALP >2.5x ULN AND TBL >2x ULN

Abbreviations: ALP = alkaline phosphatase; ALT = alanine aminotransferase; AST = aspartate aminotransferase; INR = international normalized ratio; IP = investigational product; TBL = total bilirubin level; ULN = upper level of normal.

^a Fatigue, nausea, vomiting, right upper quadrant pain or tenderness, fever, and/or rash.

Appendix 8. American Academy of Dermatology: Criteria for the Diagnosis and Assessment of Atopic Dermatitis

Features to be considered in diagnosis of patients with atopic dermatitis:

Essential Features—Must be present:

- pruritus
- eczema (acute, subacute, chronic)
 - typical morphology and age-specific patterns*
 - chronic or relapsing history

*Patterns include:

- 1)facial, neck, and extensor involvement in infants and children
- 2)current or previous flexural lesions in any age group
- 3)sparing of the groin and axillary regions

Important Features—Seen in most cases, adding support to the diagnosis:

- early age of onset
- atopy
 - personal and/or family history
 - Immunoglobulin E reactivity
- xerosis

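### Section 8.1.2 gives its liver stopping criteria two different forces, and its restart condition cannot be applied to ALP, bilirubin or INR

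*Protocol*

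**What the plan says.** **Section 8.1.2, liver list.** The lead-in makes stopping on liver results something to be "considered by the investigator when a patient meets one of the following conditions after consultation with the Lilly designated medical monitor". Seven criteria follow, four based on ALT or AST and three on ALP. One of the ALP criteria, ALP >3x ULN, may be waived after discussion with the sponsor.

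**Section 8.1.2, NOTE.** After the haematology list comes a general instruction: "For laboratory values that meet permanent discontinuation thresholds, IP should be discontinued". An exception follows. If the investigator attributes the abnormality to a cause "due to intercurrent illness such as cholelithiasis or another identified factor, laboratory tests may be repeated". Restart, after consultation with the medical monitor, is then limited: "Only when the laboratory value meets resumption thresholds", with a reference to Table JAIP.5, once the illness or other factor has resolved.

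**Table JAIP.5 (Section 8.1.1).** There is one liver-test row. Drug is held at ALT or AST >5x ULN and may resume when both are <2x ULN and study drug is not thought to be the cause.

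**Section 8.1.1, text.** Drug interrupted for a laboratory value that the table does not cover may be restarted at the investigator's discretion.

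**Appendix 7.** The same liver thresholds stand in a column for permanent discontinuation after consultation. In the temporary-interruption column, the ALP and bilirubin rows read "No applicable criteria".

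**The concern.** Two sites with the same patient could act differently and each cite Section 8.1.2. One would weigh stopping and might continue; the other would stop. If drug is stopped and the cause resolves, one site could conclude that restart is barred because no threshold exists for the analyte, while another could rely on the investigator's discretion under Section 8.1.1.

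The situation can arise in this population. Section 9.4.3 notes that ALP may be out of range in children because of normal bone growth. Exclusion criterion [42]b lets patients with ALP at or above 2x ULN enrol after discussion with the sponsor, and the ALP stopping criteria begin at >2.5x ULN. Section 3.3 names hepatotoxicity as an important potential risk.

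There is also a link to the analysis. Under Section 10.3.1 a patient who discontinues study treatment counts as a nonresponder from then on, so the reading that a site adopts can change a patient's recorded response.

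**Working it through.** No arithmetic beyond counting applies, and the protocol gives no figure to reproduce. The check sets the texts side by side.

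**Step 1: does the NOTE cover liver values?** It follows the haematology list, so it could be read as confined to that list. Two things tell against this. It speaks of laboratory values meeting permanent thresholds without naming a list, and its worked example is a biliary illness, which would explain abnormal liver tests rather than a low blood count. Appendix 7 also places the liver thresholds under permanent discontinuation, the term that the NOTE uses.

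**Step 2: compare the force of the three statements.**

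| Place | What happens when a liver criterion is met |
|---|---|
| 8.1.2, lead-in to the list | Investigator considers stopping, after consultation |
| 8.1.2, NOTE | Drug should be stopped |
| Appendix 7 | Permanent discontinuation, after consultation |

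The first leaves the outcome open; the second does not. The third makes consultation a precondition but does not present stopping as only a consideration. The sponsor waiver on ALP >3x ULN makes most sense if stopping is the default, which again differs from the lead-in.

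**Step 3: apply the restart condition to each criterion.** The NOTE requires a Table JAIP.5 resumption threshold.

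| Criterion in 8.1.2 | Resumption threshold available |
|---|---|
| ALT/AST >8x ULN | Yes, ALT and AST <2x ULN |
| ALT/AST >5x ULN for more than 2 weeks | Yes, the same |
| ALT/AST >3x ULN with bilirubin >2x ULN or INR >1.5 | ALT/AST part only; none for bilirubin or INR |
| ALT/AST >3x ULN with symptoms | Yes for ALT/AST; symptoms are not a laboratory value |
| ALP >3x ULN | None |
| ALP >2.5x ULN with bilirubin >2x ULN | None |
| ALP >2.5x ULN with symptoms | None |

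Four criteria are ALT/AST-based and three ALP-based: 4 + 3 = 7. The three ALP criteria have no threshold at all, and one ALT/AST criterion has one for only part of what triggered it. By contrast, all four haematology criteria (white cells, neutrophils, lymphocytes, haemoglobin) have a resumption value in the table, so the NOTE works for them.

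**Step 4: does Section 8.1.1 fill the gap?** Its discretionary restart applies to temporary interruptions for values outside the table. The NOTE governs values that reached a permanent threshold, and its condition is exclusive. For ALP, a site that pauses drug while consulting could place itself under either text, and they give different answers.

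**Step 5: drug status during consultation.** The lead-in puts consultation before the decision. Section 8.1.1 permits interruption outside the table and recommends consulting the sponsor first, except in an emergency. Section 9.4.9.1 calls for repeat testing within 3 to 5 days at ALT of 3x ULN or more, or at its ALP or bilirubin limits. None of these says whether dosing continues meanwhile once a Section 8.1.2 criterion has been met.

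**The case against.** The best defence is that Section 8.1.2 has two tiers: consult and decide for liver tests, stop outright for haematology, with the specific liver sentence governing the general NOTE. Appendix 7 also makes stopping conditional on consultation. This shows what may have been intended, but the cholelithiasis example prevents the NOTE from being confined to haematology, so the texts still need aligning.

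Four stronger inferences are tempting and are not supported:

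- **That the missing hold rows are themselves an error.** Appendix 7 states openly that ALP and bilirubin have no interruption criterion, and a criterion leading straight to permanent stopping needs no separate hold.
- **That the combined ALT/AST criteria have no resumption threshold.** They have one for the transaminase part.
- **That a patient with, say, ALT 4x ULN and bilirubin 2.5x ULN is unprotected.** Section 8.1.1 allows interruption outside the table, at once in an emergency, and Section 9.4.9.1 triggers prompt retesting. What is missing is a clear statement of drug status, not every safeguard.
- **That the primary endpoint is materially affected.** The protocol gives no rate of liver-related stopping. Section 3.3 reports that no hepatotoxicity cases had been identified and that most enzyme and bilirubin rises improved with continued use or a temporary stop.

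**Conclusion.** The protocol is inconsistent on two counts. First, all seven liver criteria carry both a discretionary and a directive instruction within Section 8.1.2, with Appendix 7 giving a third formulation. Second, the NOTE's exclusive restart condition cannot be applied as written to ALP (including ALP >3x ULN alone), bilirubin or INR, and it sits badly with the discretionary restart in Section 8.1.1.

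The first count rests on reading the NOTE as covering liver values, which its own example supports. The second needs only Table JAIP.5 and the NOTE; its practical reach depends on how often the ALP, bilirubin or INR criteria are met, which the protocol does not say. The importance lies in patient safety and uniform conduct across sites. Any effect on Week 16 response is unquantified and probably confined to few patients.

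**What to change.** Reconcile Section 8.1.1, Section 8.1.2 (list and NOTE), Table JAIP.5 and Appendix 7 so that:

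1. the liver criteria have one stated force everywhere, and the NOTE says explicitly whether it applies to them;
2. the status of study drug between meeting a criterion and completing the consultation is stated;
3. the restart reference works for every listed analyte, and its relation to the discretionary restart in Section 8.1.1 is made explicit, including which value counts when a criterion involves two analytes.

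Which clinical rule to adopt, including any threshold, is for the sponsor's medical team. The cost is wording in two sections, one table and one appendix, with a notice to sites. No change to the design, sample size or planned analyses is needed.

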8.1.3. Discontinuation of Inadvertently Enrolled Patients

If the Sponsor or investigator identifies a patient who did not meet enrollment criteria and was inadvertently enrolled, then the patient should be discontinued from study treatment unless there are extenuating circumstances that make it medically necessary for the patient to continue on study treatment. If the investigator and the Sponsor CRP agree it is medically appropriate to continue, the investigator must obtain documented approval from the Sponsor CRP to allow the inadvertently enrolled patient to continue in the study with or without treatment with IP. Safety follow up is as outlined in Section 2 (Schedule of Activities), Section 9.2 (Adverse Events), and Section 9.4 (Safety) of the protocol.

In some instances, it will be clear that the inadvertently enrolled patient needs to be withdrawn from the study drug. This is the case for important protocol deviations, where it is clear that the protocol deviation(s) may significantly impact the completeness, accuracy, and/or reliability of the study data or may significantly affect a subject's rights, safety, or well-being (ICH 2012). In other instances, where the protocol deviation is considered non-important since it will not significantly impact patient safety or interpretation of the study data, the Investigator and the Sponsor may agree it is medically appropriate to allow the patient to continue in the study with appropriate documentation of the rationale. Preplanned per-protocol analyses will be described in the statistical analysis plan for the study and will include analyses of key efficacy endpoints with and without data from patients with protocol deviations.

8.2. Discontinuation from the Study

Patients/parents/caregivers may choose to withdraw from the study for any reason at any time, and the reason for early withdrawal will be documented.

Patients will be discontinued in the following circumstances:

- enrollment in any other clinical study involving an IP or enrollment in any other type of medical research judged not to be scientifically or medically compatible with this study
- participation in the study needs to be stopped for medical, safety, regulatory, or other reasons consistent with applicable laws, regulations, and good clinical practice (GCP)
- study termination may occur in a specific country or region when baricitinib is approved for the treatment of AD and becomes reimbursed or commercially available in that country or region, or a negative regulatory opinion is received in that country or region
- investigator decision
 - the investigator decides that the patient should be discontinued from the study
 - if the patient, for any reason, requires treatment with another systemic therapeutic agent (not allowed as part of rescue therapy [Section 7.7.5]) that has been demonstrated to be effective for treatment of the study indication, discontinuation from the study occurs prior to introduction of the new agent.
Note: Patients rescued to systemic therapies prior to the primary endpoint (Week 16) will be encouraged to continue with study visits and assessments through Visit 8.
- subject decision
 - the patient requests to be withdrawn from the study.

Patients discontinuing from the study prematurely for any reason should complete AE and other safety follow-up per Section 2 (Schedule of Activities), Section 9.2 (Adverse Events), and Section 9.4 (Safety) of this protocol.

8.3. Lost to Follow-Up

A patient will be considered lost to follow-up if he or she repeatedly fails to return for scheduled visits and is unable to be contacted by the study site. Site personnel are expected to make diligent attempts to contact patients who fail to return for a scheduled visit or were otherwise unable to be followed up by the site.

9. Study Assessments and Procedures

Section 2 lists the Schedule of Activities, with the study procedures and their timing (including tolerance limits for timing).

Appendix 2 lists the laboratory tests that will be performed for this study.

Unless otherwise stated in the subsections below, all samples collected for specified laboratory tests will be destroyed within 60 days of receipt of confirmed test results. Certain samples may be retained for a longer period, if necessary, to comply with applicable laws, regulations, or laboratory certification standards.

9.1. Efficacy Assessments

Please refer to the Schedule of Activities (Section 2) and Appendix 6 for details on frequency of collection, method of data collection, method of administration, and age range of administration for all efficacy and health outcomes and quality-of-life measures.

9.1.1. Primary Efficacy Assessments

Validated Investigator's Global Assessment for Atopic Dermatitis (vIGA-AD): The IGA used in this study is the vIGA-AD (referred to as the IGA throughout the protocol) and measures the investigator's global assessment of the patient's overall severity of their AD, based on a static, numeric 5-point scale from 0 (clear skin) to 4 (severe disease) (information available at WWW.eczemacouncil.org). The score is based on an overall assessment of the degree of erythema, papulation/induration, oozing/crusting, and lichenification.

The IGA is a commonly used scale in clinical trials in adult and pediatric patients (Langely et al. 2015; Futamura et al. 2016).

